8.6.3. Vital Signs Parameters	20
8.6.4. 12-lead Electrocardiogram Parameters	21
8.6.5. Other Assessments	21
8.6.6. Safety and Tolerability Statistical Methodology	21
9. INTERIM ANALYSES	21
10. SIGNIFICANT CHANGES FROM THE PROTOCOL-SPECIFIED ANALYSES	21
11. REFERENCES	22
12. APPENDICES	23
Appendix 1: Document History	23

LIST OF IN-TEXT TABLES AND FIGURES

Table 1:	Presentation of Study Treatments in AE TFLs	10
Table 2:	Pharmacokinetic Treatment Labels	10
Figure 1:	Study Design	9

Covance Study: 8456071

LIST OF ABBREVIATIONS

Abbreviations pertain to the statistical analysis plan (SAP) only (not the tables, figures, and listings [TFLs]).

ADaM Analysis Data Model

AΕ adverse event

Ae amount excreted in urine per sampling interval

area under the concentration-time curve from hour 0 to 24 hours AUC₀₋₂₄ area under the concentration-time curve from hour 0 to the last AUC_{0-t}

measurable concentration

area under the concentration-time curve over a dosing interval AUC_{tau}

ARAUC accumulation ratio base on AUCtau

BID twice daily

BLO below the limit of quantification

CDISC Clinical Data Interchange Standards Consortium

maximum observed plasma concentration C_{max}

CL/F apparent systemic clearance

 CL_R renal clearance

 C_{max} maximum observed plasma concentration

COVID-19 coronavirus disease 2019 **CRU** Clinical Research Unit **CSR** clinical study report

CTCAE Common Terminology Criteria for Adverse Events

CV coefficient of variation **DMP** data management plan **ECG** electrocardiogram

eCRF electronic case report form

EOS End of Study **End of Treatment EOT** ET **Early Termination**

Fe percentage of dose excreted in urine per sampling interval

Geom CV geometric CV Geom Mean geometric mean

ICF Informed Consent Form

ICH International Council for/Conference on Harmonisation

 λ_Z Lower start of exponential fit

 $\lambda z N$ number of data points included in the log-linear regression λ_Z Span Ratio time period over which λ_Z was determined as a ratio of $t_{1/2}$

 λ_Z Upper end of exponential fit

LSM least squares mean

MedDRA Medical Dictionary for Regulatory Activities

MRT_{last} mean residence time based on AUC_{0-t}

NA not applicable

NC not calculated

NR not reported

P-gp P-glycoprotein

PK pharmacokinetic(s)

QD once daily

QTcF QT interval corrected for heart rate using Fridericia's formula

R²-adj adjusted coefficient for determination of exponential fit

SAE serious adverse event
SAP statistical analysis plan
SD standard deviation

SDV source document verification
TEAE treatment-emergent adverse event

TFL table, figure, and listing

t_{max} time to maximum observed plasma concentration
WHODrug World Health Organization Drug Dictionary

1. INTRODUCTION

This SAP has been developed after review of the clinical study protocol (Final Version 1.0 dated 12 February 2021) and electronic case report form (eCRF).

This SAP describes the planned analysis of the pharmacokinetic (PK), safety, and tolerability data from this study. A detailed description of the planned TFLs to be presented in the clinical study report (CSR) is provided in the accompanying TFL shells document.

In general, the analyses are based on information from the protocol, unless they have been modified by agreement with Loxo Oncology, Inc. A limited amount of information about this study (eg, objectives, study design) is given to help the reader's interpretation.

This SAP must be finalized prior to the lock of the clinical database. Additionally, the SAP and TFL shells should be finalized prior to any programming activities commencing.

This SAP supersedes any statistical considerations identified in the protocol; where considerations are substantially different, they will be so identified. If additional analyses are required to supplement the planned analyses described in this SAP, they may be performed and will be identified accordingly in the CSR. Any substantial deviations from this SAP will be agreed with Loxo Oncology, Inc. and identified in the CSR.

This SAP is written with consideration of the recommendations outlined in the International Conference on Harmonisation (ICH) E3 guideline *Structure and Content of Clinical Study Reports*, ICH E8 guideline *General Considerations for Clinical Trials*, ICH E9 guideline *Statistical Principles for Clinical Trials*. ^{1,2,3}

The document history is presented in Appendix 1.

2. STUDY OBJECTIVES

2.1. Primary Objectives

The primary objectives of the study are:

- to assess the effect of single and multiple oral doses of LOXO-305 on the PK of multiple oral doses of digoxin (P-glycoprotein [P-gp] substrate) in healthy subjects.
- to assess the PK of LOXO-305 administered with multiple doses of digoxin at steady state in healthy subjects.

2.2. Secondary Objective

The secondary objective of the study is to assess the safety and tolerability of single and multiple oral doses of LOXO-305 when coadministered with multiple oral doses of digoxin.

3. STUDY ENDPOINTS

3.1. Primary Endpoints

The following PK parameters will be calculated whenever possible, based on the plasma concentrations of digoxin and LOXO-305 (as appropriate):

- area under the concentration-time curve from hour 0 to the last measurable concentration (AUC_{0-t})
- area under the concentration-time curve over a dosing interval (AUC_{tau})
- apparent systemic clearance (CL/F)
- maximum observed plasma concentration (C_{max})
- time to maximum observed plasma concentration (t_{max})
- mean residence time based on AUC_{0-t} (MRT_{last})

The following PK parameters will be calculated whenever possible, based on the urine concentrations of digoxin:

- amount excreted in urine per sampling interval (Ae)
- percentage of dose excreted in urine per sampling interval (t_1-t_2) , where $\%f_{eu} = 100$ $(A_{eu}/dose)$
- renal clearance (CL_r)

3.2. Secondary Endpoints

Safety and tolerability will be assessed by monitoring adverse events (AEs), performing physical examinations and clinical laboratory evaluations, measuring vital signs, recording 12-lead electrocardiograms (ECGs), and safety monitoring of serum digoxin levels.

[figure not shown]
4. STUDY DESIGN

This is a Phase 1, open-label, fixed-sequence drug-drug interaction study to investigate the effect of single and multiple oral doses of LOXO-305 on the PK of multiple oral doses of digoxin (P-gp substrate) in healthy subjects.

On Day 1, subjects will be administered oral 0.25 mg digoxin twice daily (BID) (loading dose), once in the morning and evening. Subjects will be fasted for at least 2 hours predose and 1-hour postdose for the morning and evening dose.

On Days 2 through 16, oral doses of 0.25 mg digoxin once daily (QD) will be administered (total of 17 consecutive doses) at the actual time of the Day 1 morning digoxin dose (\pm 1 hour). On Days 8 through 16 (9 consecutive doses), oral doses of

200 mg LOXO-305 QD will be coadministered with 0.25 mg digoxin QD, at the actual time of the Day 1 morning digoxin dose (± 1 hour). LOXO-305 will be administered first, immediately followed by digoxin. On Days 2, 4 through 6, 9 through 11, 13, and 14, subjects will fast for at least 2 hours predose and 1-hour postdose. On Days 3, 12, and 15 where clinical laboratory evaluations are performed, subjects will fast for at least 8 hours predose and 1-hour postdose. On Days 7, 8, and 16, subjects will be fasted at least 10 hours predose and 2 hours postdose. Blood and urine samples for concentrations of digoxin in plasma and urine and CCI

The start of the study is defined as the date the first subject who is enrolled in the study signs an Informed Consent Form (ICF). Note that enrolled subjects are defined as those subjects who are assigned to receive a dose of study drug; this definition excludes screen failure subjects. Replacement subjects may be enrolled only if deemed necessary by the Sponsor.

Subjects who are determined to be screen failures are permitted to be re-screened if the Investigator (or designee), with agreement from the Sponsor, feels that the subject may meet eligibility criteria upon re-screen. Re-screened subjects will be provided a new subject number.

To assess their eligibility to enter the study, potential subjects will be screened within 28 days (Days -29 to -2) and be admitted to the Clinical Research Unit (CRU) on Day -1 (Check-in).

Subjects will be confined at the CRU from the time of Check-in (Day -1) until End of Treatment (EOT) on Day 20 upon completion of all PK and safety assessments or Early Termination (ET) if the subject discontinues. Dosing of digoxin will occur on Days 1 through 16 and dosing of LOXO-305 will occur on Days 8 through 16. A follow-up phone call will occur for all subjects who received at least 1 dose of study drug (including subjects who are terminated early) 7 days (\pm 2 days) after EOT or ET. The duration of participation is expected to be approximately 58 days (Screening through follow-up phone call).

In this study, physical examinations, 12-lead ECGs, vital sign measurements, How Do You Feel? inquiries, clinical chemistry panel, coagulation parameters, hematology panel, urinalysis, safety monitoring of serum digoxin levels, and recording of concomitant medications will be performed at specified times during the study.

[figure not shown]
The AEs and serious adverse events (SAEs) will be collected beginning at informed consent. The AEs will be reported throughout the study (ie, from signing of the ICF until End of Study [EOS], or until ET if the subject discontinues from the study and does not complete a follow-up phone call), either as subject medical history (if the event is reported as beginning prior to signing of the ICF or if the event occurs prior to study drug administration on Day 1 and is

assessed as not related to study procedures by the Investigator [or designee]) or as AEs (if the event occurs after signing of the ICF but prior to study drug administration on Day 1 and is assessed as related to study procedures by the Investigator [or designee], or if the event occurs after study drug administration on Day 1 through EOT or ET regardless of relationship to study drug). From EOT or ET through EOS, only AEs assessed as related to study drug by the Investigator (or designee) are to be reported. All SAEs that develop from the time of ICF signing until EOS (or ET, if the subject discontinues from the study and does not complete a follow-up phone call) are to be reported.

Study completion is defined as the time of the last subject's follow-up phone call.

A schematic of the study design is presented in Figure 1.

Figure 1: Study Design

BID = Twice daily; QD = Once daily; EOT=End of treatment; ET= Early termination

5. SAMPLE SIZE JUSTIFICATION

Up to 16 healthy adult male and female subjects (women of non-childbearing potential only) will be enrolled. The sample size chosen for this study was selected without statistical considerations but is consistent with previous studies of a similar design. Up to 16 subjects are anticipated to be sufficient to provide a reliable estimate of the magnitude and variability of the interaction. Replacement subjects may be enrolled only if deemed necessary by the Sponsor. Every attempt will be made to enroll at least 4 subjects of each sex in the study.

6. STUDY TREATMENTS

The study treatment names and ordering to be used in the TFLs are presented in Table 1.

Table 1: Presentation of Study Treatments in Safety TFLs

Study Treatment	Order in TFLs
0.25 mg Digoxin Alone	1
200 mg LOXO-305 QD + 0.25 mg digoxin QD	2

OD = once daily; TFL = table, figure, and listing.

All TFLs will be based on actual treatments.

Table 2 shows a list of the PK treatment labels and ordering that will be used in the TFLs.

Table 2: Pharmacokinetic Treatment Labels

Study Treatment Labels	Order in TFLs
0.25 mg Digoxin Alone	1
200 mg LOXO-305 Once + 0.25 mg digoxin QD	2
200 mg LOXO-305 QD + 0.25 mg digoxin QD	3

QD = once daily; TFL = table, figure, and listing.

The study treatment sequence names and ordering to be used in the TFLs are presented in Table 3.

Table 3. Presentation of Study Treatment Sequences in TFLs

Study Treatment Sequence	Order in TFLs
0.25 mg Digoxin BID (D1) / 0.25 mg Digoxin QD (D2-7) / 200 mg LOXO-305 QD + 0.25 mg digoxin QD (D8-D16)	1

BID = twice daily; QD = once daily; TFL = table, figure, and listing.

7. DEFINITIONS OF POPULATIONS

Any protocol deviations, including those due to coronavirus disease 2019 (COVID-19) and related restrictions (see Section 8.1.1), will be considered prior to database lock for their importance and taken into consideration when assigning subjects to populations.

7.1. All Subjects Population

The all subjects population will consist of all subjects who signed the ICF and had any study assessment recorded in the database per the protocol.

7.2. Safety Population

The safety population will consist of all subjects who received at least 1 dose of study drug (digoxin and/or LOXO-305).

7.3. Pharmacokinetic Population

The PK population will consist of all subjects who received a dose of LOXO-305 or digoxin, have at least 1 quantifiable plasma concentration, and for whom at least 1 PK parameter can

be computed. A subject may be excluded from the PK summary statistics and statistical analysis if the subject has an AE of vomiting that occurs at or before 2 times the median t_{max} . The impact of protocol deviations on the PK population will be evaluated on a case-by-case basis.

8. STATISTICAL METHODOLOGY

8.1. General

Listings will be provided for all data captured in the database. Listings will include all subjects assigned to the all subjects population and include data up to the point of study completion or discontinuation. Subjects are generally considered to have completed the study if they completed all protocol-specified procedures and assessments for the EOS visit. Any subject who discontinues the study will be identified accordingly in the listings. Summaries and statistical analyses will include the subjects assigned to the relevant population based on data type.

Data analysis will be performed using the SAS® statistical software package Version 9.4 (or higher if a new version is issued during the study).

Analysis Data Model (ADaM) datasets will be prepared using Clinical Data Interchange Standards Consortium (CDISC) ADaM Version 2.1 (or higher if a new version is issued during the study) and CDISC ADaM Implementation Guide Version 1.2 (or higher if a new version is issued during the study). Pinnacle 21 Community Validator Version 3.1.0 (or higher if a new version is issued during the study) will be utilized to ensure compliance with CDISC standards.

For all statistical analyses, the hypothesis testing will be 2-sided and carried out on 0.05 significance level, unless specifically stated otherwise.

Caution should be used when interpreting results from the statistical analyses conducted in this study because the sample size is not based on power calculations.

Where reference is made to 'valid' data, this refers to non-missing data which meet the predetermined criteria (eg, are not flagged for exclusion).

Where reference is made to 'all calculations', this includes, but is not limited to, summary statistics, statistical analyses, baseline derivation and changes from baseline.

All figures will be produced on linear-linear or discrete-linear scales, as applicable, unless specifically stated otherwise.

8.1.1. Handling of Data Quality Issues Due to Coronavirus Disease 2019 and Related Restrictions

Due to COVID-19 and related restrictions, there is a high risk for impact to data integrity, with the recognized potential for:

• Missed visits, caused by, for example:

- Subject unable to travel to site due to restrictions, the need to quarantine, or COVID-19 infection
- o Subject unwilling to go to site due to fear of COVID-19 infection
- Site postponing subject's visit due to investigator not being available (eg, if they have been dispatched to hospital handling COVID-19 infections)
- Site unable to replenish supply of investigational product
- Incomplete data entry by sites due to limited resources to support study or no access to source documents or to eCRF
- Outstanding source document verification (SDV) due to sponsor or country restrictions on remote SDV, or no or limited access to site(s) for on-site visits
- Unanswered queries

At the time of the reporting of the study results, all protocol deviations due to COVID-19 or related restriction will be assessed for their severity and impact on the analyses. If needed, appropriate statistical methods will be applied as a mitigating action (eg, data might be categorized into 2 analysis groups, with and without COVID-19 and related restrictions impact); however, this will exclude any imputations of the missing values. Any mitigating actions will be agreed with Loxo Oncology, Inc. in advance and identified in the CSR.

8.1.2. Calculation of the Summary Statistics

For continuous data the following rules will be applied:

- Missing values will not be imputed, unless specifically stated otherwise.
- Unrounded data will be used in the calculation of summary statistics.
- If the number of subjects with valid observations (n) <3, summary statistics will not be calculated, with the exception of n, minimum, and maximum.
- In general, as ET data are not associated with any scheduled timepoint, they will be excluded from all calculations of summary statistics and statistical analyses. Exceptions may be made where justified.
- Postdose repeats and unscheduled assessments will not be included in calculations of summary statistics.

For categorical data the following rules will be applied:

• For ordered categorical data (eg, AE severity), all categories between the possible minimum and maximum categories will be included, even if n = 0 for a given category.

• For non-ordered categorical data (eg, race), only those categories for which there is at least 1 subject represented will be included; unless specifically stated otherwise.

• Missing values will not be imputed, unless specifically stated otherwise. A 'missing' category will be included for any parameter for which information is missing. This will ensure that the population size totals are consistent across different parameters.

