4.6. Removal of Subjects from Study Participation

Subjects will be informed that they are free to withdraw from the study at any time and for any reason. The Investigator (or designee) may remove a subject from the study if, in the Investigator's (or designee's) opinion, it is not in the best interest of the subject to continue the study. Subjects may be withdrawn because of the following:

 change in compliance with inclusion/exclusion criterion that is clinically relevant and affects subject safety

- occurrence of AEs
- occurrence of pregnancy
- non-compliance with study restrictions
- intake of non-permitted concomitant medication that might affect subject safety or study assessments/objectives, etc.

Notification of withdrawal will immediately be made to the Sponsor. In case of withdrawal, efforts will be made to perform all ET assessments (Appendix 4). The date the subject is withdrawn from the study and the reason for withdrawal will be recorded on the subject's electronic Case Report Form (eCRF). All withdrawn subjects with AEs that are assessed as related to study drug and which are ongoing at ET may continue to be followed until the symptoms or value(s) return to normal, or acceptable levels, as judged by the Investigator (or designee) and confirmed by the Sponsor.

The entire study may be discontinued at the discretion of the Investigator (or designee) or Sponsor, based on the occurrence of the following:

- AEs unknown to date with respect to their nature, severity, and/or duration
- increased frequency and/or severity and/or duration of known AEs
- medical or ethical reasons affecting the continued performance of the study
- difficulties in the recruitment of subjects
- cancellation of drug development.

In the event that the study is terminated early, the Sponsor or its designee will provide specific guidance to the CRU regarding the EOS procedures.

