8.1.3. Repeat and Unscheduled Readings

For vital signs measurements and 12-lead ECG data only, any predose value recorded in addition to the original value or a postdose value recorded within 15 minutes of the original value will be defined as a repeat value; any postdose value recorded more than 15 minutes after the original value will be defined as an unscheduled value. For all other data types (eg, laboratory parameters), any value recorded in addition to the original value will be defined as an unscheduled value.

The original scheduled value will be used in all calculations post dose. In the event of any repeats or unscheduled measurements taken pre-dose the values will be considered when determining the baseline value.

As unscheduled values are not associated with any scheduled timepoint, they will be excluded from all calculations, with the exception of the baseline derivation (see Section 8.1.4).

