8.6.3. Vital Signs Parameters

All vital signs parameters and their changes from baseline will be listed, as applicable; any value outside the clinical reference range will be flagged, and whether the out of range value was deemed clinically significant or not clinically significant will be indicated.

Summary tables by treatment and timepoint will be provided for all vital signs parameters and their changes from baseline, as applicable.

8.6.4. 12-lead Electrocardiogram Parameters

All 12-lead ECG parameters and their changes from baseline will be listed; any value outside the clinical reference range will be flagged, and whether the out of range value was deemed clinically significant or not clinically significant will be indicated.

Summary tables by treatment and timepoint will be provided for all 12-lead ECG parameters, along with their changes from baseline.

QT interval corrected for heart rate using Fridericia's formula (QTcF) values that are > 450 msec and increase from baseline > 30 msec will be flagged in the data listing.

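### The SAP leaves early-termination (by default) and unscheduled values out of the continuous safety summaries, and its bar on change from baseline for unscheduled values disables the QTcF flag for an unscheduled ECG

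*SAP*

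**What the plan says.** SAP 8.1.2, under the rules for continuous data, states that, in general, "as ET data are not associated with any scheduled timepoint, they will be excluded from all calculations of summary statistics and statistical analyses". The next sentence reads "Exceptions may be made where justified" and gives no criteria. A separate bullet has no exception clause: "Postdose repeats and unscheduled assessments will not be included in calculations of summary statistics".

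SAP 8.1.3 says of unscheduled values that "they will be excluded from all calculations, with the exception of the baseline derivation". SAP 8.1 defines the term *all calculations*: "this includes, but is not limited to, summary statistics, statistical analyses, baseline derivation and changes from baseline".

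SAP 8.6.2 and 8.6.4 list all laboratory and ECG parameters with their changes from baseline. SAP 8.6.3 does the same for vital signs, as applicable. All three flag out-of-range values and state their clinical significance. Their summary tables are by treatment and timepoint. Under 8.6.4, a QTcF value above 450 msec with an "increase from baseline > 30 msec will be flagged in the data listing".

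Protocol 4.6 asks sites to attempt all ET assessments when a subject is withdrawn. Appendix 4 includes an ECG, vital signs and clinical laboratory tests among them.

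**The concern.** Safety and tolerability of coadministration is the secondary objective. Under Protocol 7.2.6, a trough serum digoxin level above 2.0 ng/mL, or clinically significant signs or symptoms of toxicity, may lead to discontinuation. The measurements taken when such a problem arises are likely to be unscheduled or ET values, and those are the two kinds that the SAP treats differently from scheduled values.

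Two things are at stake. First, the continuous summaries would by default describe scheduled values only, and whether an ET value is ever added would be decided without a stated rule in an open-label study. Second, the listing is the place where these values are meant to remain visible, yet its one change-based warning, the QTcF flag, would not work for an unscheduled ECG.

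**Working it through.** **Inputs.** The rules come from SAP 8.1, 8.1.2, 8.1.3 and 8.6.2 to 8.6.4, and the ECG times from Protocol Appendix 4. There is no plan figure to reproduce: the sample of up to 16 was chosen without statistical considerations, and no safety inference is planned.

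**Step 1: each kind of postdose value under the rules, read literally.**

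| Value | Summary by timepoint | Change from baseline in listing | QTcF flag | Listed, with out-of-range flag |
|---|---|---|---|---|
| Scheduled | Included | Derived | Can be set | Yes |
| Repeat (vital signs, ECG) | Excluded, no exception | Not expressly barred, but 8.1.3 bases all postdose calculations on the original scheduled value | Doubtful | Yes |
| Unscheduled | Excluded, no exception | Barred by 8.1.3 with 8.1 | Cannot be set | Yes |
| ET | Excluded by default | Not barred by 8.1.2, which names only summary statistics and statistical analyses | Can be set | Yes |

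The unscheduled row holds the contradiction. Sections 8.6.2 and 8.6.4 call for a listed change for all parameters, while 8.1.3 forbids computing it for some of them. A programmer cannot follow both. The reason given in 8.1.3, that the value belongs to no scheduled timepoint, justifies keeping it out of a by-timepoint table. It does not justify withholding the change, which needs only the value and the baseline. If the two QTcF conditions were read as separate flags, the one for the increase would still be lost.

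**Step 2: when an ECG would be unscheduled.** Coadministration runs over Days 8 to 16, which is 9 days. ECGs are scheduled on 5 of them: Days 8, 10, 12, 15 and 16. None is scheduled on the other 9 − 5 = 4: Days 9, 11, 13 and 14. On Days 10, 12 and 15 the only scheduled ECG is predose, so an additional ECG after that day's dose would normally be unscheduled too. Safety digoxin samples are taken predose daily on Days 7 to 15, so a high level can come to light on days without a scheduled ECG.

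**Step 3: whether another table catches these values.** Sections 8.6.2 to 8.6.4 specify no worst-value, shift or outlier table. The TFL shells are a separate document and are not available here.

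**Step 4: how often ET might occur.** The documents give no rate, so 5%, 10% and 20% are assumptions. With 16 subjects, P(at least one ET) = 1 − (1 − p)^16:

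- p = 0.05: 1 − 0.440 = 0.56
- p = 0.10: 1 − 0.185 = 0.81
- p = 0.20: 1 − 0.028 = 0.97

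The binomial probability of at least three is 0.04, 0.21 and 0.65. SAP 8.1.2 reports only n, minimum and maximum when n is below 3, so at the two lower rates a separate ET row would usually show little. These rates cover ET for any reason, not only poor tolerability.

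**The case against.** The strongest reply is that nothing is hidden. SAP 8.1 lists all data in the database and identifies discontinued subjects. Out-of-range values are flagged, and that flag needs no baseline; 8.6.2 even names listing flags separately from calculations. Under Protocol 7.2.1, adverse events noted on ECG, vital signs or laboratory tests are recorded as such, and SAP 8.6.1 tabulates treatment-emergent events leading to discontinuation. With at most 16 subjects a reader can go through the listings. The ET rule is only a default, and the SAP introduction requires substantial deviations to be agreed and identified in the study report. Protocol 8.4 promises descriptive summaries where possible, not a worst-value table.

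Most of this stands, and it limits the point. It does not resolve the conflict between 8.1.3 and 8.6.2 to 8.6.4, and relying on the listings is weaker when the listing's own QTcF flag is switched off for unscheduled ECGs.

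Three stronger readings are tempting, and the documents do not support them:

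- *Data from stopped subjects disappear from the safety results.* They are listed and flagged, the subject's earlier scheduled values stay in the tables, and the adverse-event tables are unaffected.
- *ET values are also barred from change from baseline.* The ET rule does not say so.
- *The bias can be put at a number.* A 60 msec QTcF rise at ET in one of 16 subjects would move a mean by 60/16 = 3.75 msec, but the rise is invented, and so is any assumption of no change elsewhere. The loss of 1/16 = 6.25% of subjects from later timepoints follows from the subject leaving, and including the ET value would not fill those timepoints.

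**Conclusion.** The point holds in a limited form. By default, laboratory, vital-sign and ECG values taken at ET enter no continuous summary that the SAP specifies, and the exception has no criteria. Postdose repeat and unscheduled values are excluded outright. For unscheduled values, change from baseline is barred in one section and called for in others, and the QTcF flag cannot be set.

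The loss is confined to the laboratory, vital-sign and ECG summary tables and to the change-based items in the listings. Its size is unknown, because the documents give neither an ET rate nor a frequency of unscheduled tests. A reader might infer that coadministration will look safer than it is. That would require stops to be related to tolerability and the omitted values to be worse than the scheduled ones. Both are plausible, but neither is shown: stopping for digoxin level or toxicity is discretionary, and Protocol 4.6 also lists reasons unrelated to tolerability.

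The conclusion rests on a literal reading of 8.1.3 and on the TFL shells not already containing a table of extreme values. The primary pharmacokinetic comparison is not affected.

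**What to change.** 1. Amend SAP 8.1.3 so that change from baseline and the QTcF flag are derived in the listings for every postdose value: scheduled, repeat, unscheduled and ET. This removes the conflict with 8.6.2 to 8.6.4.
2. Keep the scheduled-timepoint tables as they are.
3. Add to 8.6.2 to 8.6.4 one descriptive row per parameter and treatment, summarizing each subject's most extreme postdose value and change from baseline. Use all postdose values, including ET, assigned to the treatment being received at the time. State for each parameter whether extreme means highest, lowest or both. ET values then enter by rule, so no case-by-case exception is needed for them.
4. Footnote that subjects tested more often have more chances of an extreme value.

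The cost is SAP wording, matching shells and a few table rows, all from data already collected. The downside is the one in the footnote. For ECGs, the scheduled counts do not add to it in subjects who complete. There are 8 postdose ECGs before the first LOXO-305 dose (Day 1 at 2 hours, Days 2 to 7, Day 8 predose: 1 + 6 + 1). There are 8 after it (Day 8 at 2 hours, Days 10, 12 and 15, Day 16 twice, Days 18 and 20: 1 + 3 + 2 + 2). For laboratory tests the scheduled counts are 2 (Days 3 and 7) and 3 (Days 12, 15 and 19), which the footnote should mention.
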